7.0 STATISTICAL ANALYSES

Aim 1. Aim 1 of the proposed pilot study will evaluate the feasibility and acceptability of the proposed intervention. The feasibility of the study will be assessed by the following criteria displayed in Table 1.

Table 1. Feasibility and acceptability measures and benchmarks.

FEASIBILITY		
	Measure	Benchmark
Recruitment	Enrollment rate	7 participants/month
Intervention Adherence	Response rate to intervention messages Response rate to EMA prompts Fitbit use (% of days with > 8 hours wear time)	75% 75% 70%
Retention	Completion of follow-up assessments	90%
ACCEPTABILITY		
	Measure	Benchmark
Intervention satisfaction	Satisfaction questionnaire	75% of participants rate ≥ 4 on 5-point Likert scale

Aim 2.

Hypothesis 2a: *Participants will have greater daily step counts on days receiving an affective framing message compared to non-message days.*

A repeated-measures mixed effects model will be used as described in Klasnja et al. (2015) with participant and time as random effects and other effects as fixed. Daily step count will be the dependent variable while main effects of affective framing intervention (message/no message) and linear time effects will be within-subjects factors, and an intervention by time interaction term will be included. We also will consider more complex effects of time (e.g., quadratic effects). We will include scores of the Physical Activity Intention, Physical Activity Self-Efficacy, and Affect as time-varying covariates. As described in Klasnja, et al. (2015) we will include the scores for the day prior to the intervention so the covariates will not be affected by the intervention. We will also classify each day as a cancer treatment day (i.e. day on which chemotherapy or radiation therapy is received) or not and presence/absence of cancer treatment will also be a time-varying covariate. A time lag is not needed for this covariate as the timing of cancer treatment will not be influenced by the intervention. Presence/absence of an implementation planning message on each day will also be included as a time-varying covariate and an affective framing by planning message interaction will be included to assess synergistic effects of the two messages. The baseline measurement of theoretical moderators of physical activity behavior change (Physical Activity Stage of Change, Physical Activity Self-Efficacy, Multidimensional Outcome Expectations for Exercise Scale) and psychosocial characteristics Functional Assessment of Cancer Therapy – General, Quick Inventory of Depressive Symptomatology – Self-Rated, Brief Fatigue Inventory) will be considered as covariates as will other baseline demographic and clinical variables determined to improve the fit of the final model.

Hypothesis 2b: *Participants will have greater daily step counts on days receiving the implementation planning message compared to non-message days.*

The same repeated-measures mixed effects model described for Hypothesis 2a will be used for this hypothesis. Only the interpretation of the results will be different as the presence/absence of the implementation message will be the main effect and the affective framing intervention will be considered the covariate.

Hypothesis 2c: Participants randomized to receive feedback prompts reporting their highest daily step count will achieve greater step counts compared to participants that receive feedback prompts reporting their average daily step counts.

Participants will be randomized at baseline for the duration of the study because we expect that the intervention will have a cumulative effect over the course of the study. The hypothesis will be tested using a repeated-measures mixed effects model with participant and time as random effects and other effects as fixed. Daily step count will be the dependent variable. The intervention (highest vs average steps feedback) will be a between-subjects factor and time the within-subjects factor and an intervention by time interaction term will be included. We also will consider more complex effects of time (e.g., quadratic effects). The baseline characteristics described in Hypothesis 2a will be considered to improve the fit of the final model. We will also consider the inclusion of time-varying covariates if a clinically meaningful imbalance between groups is found.

Exploratory analyses

For Aim 2a and 2b we will also evaluate the moderating effects of time-varying factors measured through daily EMA (Physical Activity Intention, Physical Activity Self-Efficacy, and Affect). Our ultimate goal is to be able to evaluate these factors to inform decision rules in the ultimate adaptable intervention. The proposed sample size limits the power to detect time-varying moderators of intervention effects and formal analysis of moderating effects will only be conducted in the subsequent clinical trial. These analyses will use a repeated-measures mixed effects model as described above for Hypotheses 2a and 2b, and the moderating effect will be represented by a 3-way interaction of intervention, covariate, and time.

Power calculations

The study design for Aims 2a and 2b will require subjects to be randomized each day to receive the intervention or not. Each day there will be a 50% probability of receiving the intervention (1:1 randomization schedule) so that the average subject will receive the intervention on 28 of the 56 study days. The sample size for Hypotheses 2a and 2b of 50 is based on the sample sizes in the table below which assume 80% power with an alpha=0.05. We also assume that the effect size (standardized difference between treatment groups, similar to Cohen's d) is constant during the 56-day study period. Note that for Cohen's d an effect size of 0.2 or less is considered 'small' (Cohen, 1998) (small effect=0.2, medium effect=0.5, large effect=0.8), therefore, the proposed sample size of 50 will be able to detect effect sizes that are about half of a 'small' effect.

The power analysis for Hypothesis 2c is based on a repeated measures analysis of variance comparison of two groups with 56 repeated observations assuming a correlation between repeated measurements of 0.5, 80% power, and alpha=0.05. Given these assumptions, an effect size of 0.29 can be detected with the proposed sample size of 50. Based on Cohen's guidelines for an ANOVA f-test an effect size of 0.29 is slightly larger than a 'medium' effect (small effect=0.1, medium effect=0.25, large effect=0.4).

Table 1. Sample size calculations.

Hypotheses 2a and 2b		Hypothesis 2c	
Effect Size	Sample Size to Obtain 80% Power	Effect Size	Sample Size to Obtain 80% Power
0.200	17	0.290	50
0.109	50	0.265	60
0.099	60	0.245	70
0.091	70	0.203	100
0.076	100	0.100	402

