Each morning during the eight-week intervention, participants will receive questions about their current affect, intent to engage in physical activity, and self-efficacy for engaging in physical activity. At each request, participants will be given the option to “snooze” the request for up to one hour. The assessment questions will be viewed and responded to on the Fitbit Versa device. We will utilize the Fitbase Engage platform (see Figure 3), which utilizes the Fitbit SDK to deliver assessments and message prompts via the Fitbit Versa. Assessment questions have been validated for their use in EMA.⁵⁻⁷ Daily questions will include:

Figure 3. Representations of messages delivered via the Fitbase Engage platform.

*Actual messages will be customized as described below.

Physical Activity Intention (One item; 1 strongly disagree to 5 strongly agree)

“I intend to meet my goal of XXX steps today”

Physical Activity Self-Efficacy (One item; 1 not confident at all to 5 completely confident)

“I believe I can complete my goal of XXX steps today.”

Affect (Nine items assessing positive and negative affect; 1 not at all to 5 extremely)

“How (happy, cheerful, relaxed, stressed, anxious, angry, depressed, energetic, fatigued/tired) do you feel right now?”

Affective Framing Messages. After completing the daily EMAs, participants may receive an affective framing message. Message delivery will occur on a 1:1 randomization schedule, such that participants will receive messages on 28 of the 56 intervention days. The study biostatistician will generate randomization schedules for each participant using block randomization with variable block sizes. Messages will be randomly selected from a pool of 14 messages, meaning each message will be received twice during the eight-week study. Messages will emphasize potential improvements in mood, energy, and calmness.^{8,9} Examples of these messages:

“Research has shown that physical activity often results in improved mood.”

“Most people report feeling happier and more relaxed after exercise.”

Weekly Goal Setting. Each Sunday evening, participants will receive a prompt to select a step goal for the upcoming week. Along with this prompt, participants will receive feedback on their activity during the previous week. Participants will receive either: 1) the average daily number of steps taken during the previous week, or 2) the highest daily number of steps taken during the previous week.

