Intention Planning Prompts. Delivery of these messages will occur on a 1:1 randomization schedule, such that participants will receive messages on 28 of the 56 intervention days. Planning prompts will be delivered in the evening at a time preferred by the participant. At each request, participants will be given the option to “snooze” the request for up to one hour. Using a drop-down

menu, participants will be able to indicate the time, duration, and location to complete the following prompt:

“Tomorrow, at (time), I will walk for (duration) minutes at (location).”

Activity recognition. We will utilize Fitbit SmartTrack feature to automatically detect physical activity bouts. The SmartTrack settings will be customized to identify all physical activity bouts of ≥ 10 minutes. Approximately one hour after completion of a physical activity bout, participants will be asked to report on their current affect and reflect upon their experience during the physical activity bout. Delivery of these assessments will occur after each activity bout; however, in the event of multiple activity bouts occurring in one day, assessments will be limited to the first activity bout of that day. Participants will be given the option to “snooze” for up to one hour if they are unavailable.

Affect (Nine items assessing positive and negative affect; 1 not at all to 5 extremely)

“How (happy, cheerful, relaxed, stressed, anxious, angry, depressed, energetic, fatigued/tired) do you feel right now?”

Remembered Experience (One item; 1 very good to 5 very bad).

“Think back to how you felt during your physical activity today - How do you remember feeling?”

Savoring – After completing the EMAs, participants will receive the savoring messages after 50% of their detected activity bouts (1:1 randomization schedule). Participants will receive imagery-based prompts, as those have been shown to elicit more positive affect responses compared to descriptive prompts (Nelis et al 2015). Delivery of the savoring prompts will occur over approximately 1-minute, with pauses interspersed between prompts to allow for the participant to imagine their experience (see below).

“Thinking back to that physical activity bout, try to create an image of that in your mind. Spend a moment re-living the activity.”

(10 seconds)

“Replay that memory as if you were watching a movie in mind.”

(10 seconds)

“What could you see around you?”

(10 seconds)

“What could you hear?”

(10 seconds)

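### The 2a/2b detectable effect of 0.109 at N=50 assumes almost all 56 days are analysed, and the plan does not state that share, the handling of missing prior-day EMA scores, or assignment coding

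*Combined protocol and SAP*

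**What the plan says.** **Contrast.** Section 7.0 states Hypothesis 2a as "Participants will have greater daily step counts on days receiving an affective framing message compared to non-message days". The model paragraph names the factor only as message or no message. It does not say whether that means assigned or received.

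**Delivery.** Section 5.4 says "After completing the daily EMAs, participants may receive an affective framing message". It gives no rule for a morning when the EMA is not completed. The same paragraph describes the schedule in terms of receipt: "such that participants will receive messages on 28 of the 56 intervention days", with 14 messages in the pool, "meaning each message will be received twice during the eight-week study". For the planning prompt it says "Planning prompts will be delivered in the evening at a time preferred by the participant", and the prompt's text is about the following day.

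**Covariates.** The 2a/2b model includes intention, self-efficacy and affect scores from the day before. No method is given for a missing score.

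**Benchmarks.** The feasibility table in section 7.0 lists "Response rate to EMA prompts" at 75% and days with more than 8 hours of wear at 70%.

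**Power.** The power section assumes 56 days, a 50% daily probability, a constant effect, 80% power and alpha 0.05. It tabulates 0.109 at N=50 and describes this as about half of a small effect (0.2). It states no share of usable days, and does not say whether d is scaled by the total or the within-person SD.

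**The concern.** There are two linked gaps.

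The first is about information. The detectable effect depends directly on how many participant-days enter the model. Days can be lost for lack of usable step data. They can also be lost when the previous morning's EMA was missed, if the software drops rows with a missing covariate. The plan sets adherence benchmarks well below 100% but reports a detectable effect with no allowance for loss.

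The second is about the comparison. If the framing message appears only once the EMA is completed, receipt depends on what the participant does. EMA questions are handled on the watch that also counts steps ("The assessment questions will be viewed and responded to on the Fitbit Versa device"), so a missed EMA may coincide with low wear. Coding such days as non-message days would mix participant behaviour into a contrast that was randomised. One unwritten sentence then decides whether 2a is a randomised comparison.

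**Working it through.** **Inputs.** From the power section: N=50, 56 days, daily probability 0.5, alpha 0.05, 80% power, d=0.109. From the feasibility table: 75% EMA response and 70% wear days. Assumptions: a two-sided test (sidedness is not stated) and a usable-day share s.

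**Formula.** F test on 1 and N−3 degrees of freedom, with noncentrality

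λ = N × 56 × s × 0.5 × 0.5 × d² / (1 − ρ).

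Here ρ is the within-person correlation. It enters only if d is on the total SD; ρ=0 is the table's scale.

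**Reproducing the table (s=1, ρ=0).** The smallest N for 80% power at d = 0.200, 0.109, 0.099, 0.091 and 0.076 is 17, 50, 60, 70 and 100. All five rows match. At s=0.95 they become 18, 52, 63, 74 and 105. A one-sided normal calculation gives about 37 for 0.109, so it does not fit.

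**Share needed.** At N=50, d=0.109 and s=1, λ = 50 × 56 × 0.25 × 0.109² = 8.32 and power is 81%. The smallest share that keeps 80% is 0.984, or 0.984 × 56 = 55.1 days.

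**Other shares (N=50, ρ=0).** The exact detectable effect with complete data is 0.1081, and it scales as 0.1081/√s.

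| Usable share | λ at 0.109 | Detectable effect | Power at 0.109 | Power at 0.2 |
|---|---|---|---|---|
| 0.90 | 7.49 | 0.114 | 76% | over 99% |
| 0.75 | 6.24 | 0.125 | 69% | 99% |
| 0.70 | 5.82 | 0.129 | 66% | 99% |

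As fractions of 0.2, these effects are 0.57, 0.62 and 0.65.

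**Scale of d.** If d is on the total SD, only s/(1 − ρ) matters, and it must reach 0.984. The loss is fully offset when ρ = 1 − s/0.984, which is 0.09 at 90% usable, 0.24 at 75% and 0.29 at 70%. At ρ=0.3, power at 0.109 is 83% (75% usable) and 81% (70%). At ρ=0.5, a value the plan assumes only for Hypothesis 2c, it is 93% and 92%.

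**Receipt coding, only if a missed EMA withholds the message.** At 75% response, message days fall to 56 × 0.5 × 0.75 = 21. The other days make up 1 − 0.375 = 0.625 of the total, of which missed-EMA days are 0.25/0.625 = 40%. At 90% response the figure is 0.10/0.55 = 18%. The bias would be 0.40 or 0.18 times the step difference between EMA-completed and EMA-missed days, which the documents do not give.

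**Assignment coding under the same condition.** The contrast stays randomised but is diluted, assuming an undelivered message has no effect. A delivered-day effect of 0.109 becomes 0.109 × 0.90 = 0.098 (power 72%) or 0.109 × 0.75 = 0.082 (power 56%). The detectable delivered-day effect is 0.1081/0.90 = 0.120 or 0.1081/0.75 = 0.144.

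**The case against.** **Receive mostly means scheduled.** Sections 3.1 and 5.4 and the power section all use the verb for the randomised schedule. On that reading receipt equals assignment and the coding question disappears. The statement that the message comes after the EMA gives an order; nothing says a message is withheld. This stands. A reader might infer that the 2a comparison is already broken, but the documents do not support that. The problem needs both an unstated delivery gate and coding by receipt, and the size and sign of any bias are unknown.

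**The benchmarks are not exclusion rules.** No rule drops low-wear days, and a missed EMA does not erase a step count. This also stands. The 70% and 75% shares are scenarios, and the EMA rate removes days only under complete-case fitting, which the plan neither adopts nor rules out.

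**The shortfall may not exist.** If d is on the total SD, a correlation of 0.3 removes it. This stands as well. A reader might conclude that the trial has only 66% power; that holds only on the table's scale and at a 70% share.

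**The cited methods source may settle coding or unavailable days.** It cannot be checked here. The analysis section should be explicit in any case.

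**The consequence is small.** This is a pilot, and 0.114 is still close to half of a small effect. That limits the severity. It does not remove the need to state the assumption behind 0.109, since the background section says that evaluation of these components decides which enter the later intervention.

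**Conclusion.** The point holds at minor severity.

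- The 0.109 is not an arithmetic error. It is correct on its own scale for essentially complete data (at least 98% of days), an assumption inferred from reproducing the table because the text does not state it.
- At 90%, 75% and 70% usable days, with no gain from within-person correlation, the detectable effect is 0.114, 0.125 and 0.129. Power at 0.109 is 76%, 69% and 66%. If d is on the total SD, a correlation of about 0.24 to 0.29 or more offsets the loss at 75% to 70%.
- The 2a factor is ambiguous between assignment and receipt. This harms the comparison only if a missed EMA withholds the message.

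A reader might multiply the two benchmarks (0.75 × 0.70 = 0.525) and call the resulting 0.149 a worst case. It is not one. It assumes the two losses are independent, which is doubtful when EMAs are answered on the watch. Minimum overlap (0.75 + 0.70 − 1 = 0.45) would give 0.161. Both figures also need exclusion rules that the plan does not contain.

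**What to change.** 1. Define the 2a and 2b factors as the randomised assignment, regardless of receipt. Pair each evening planning prompt with the next day's steps, since a same-day pairing would set it against steps mostly already taken. Analyse all randomised days with step data, and say how low-wear days are treated.
2. Keep days with a missing prior-day EMA score in the model by a stated method, for example a missing indicator or imputation from earlier data.
3. Restate the 2a/2b detectable effect at N=50 with an explicit usable-day share (0.109 complete, 0.114 at 90%, 0.125 at 75%, 0.129 at 70%), and say which SD d uses. Once items 1 and 2 are adopted, EMA non-response no longer removes days, so the relevant share is that of days with step data. Do not present 0.149 as a worst case.
4. State whether a missed EMA withholds the framing message. Only if it does, add a supporting 2a analysis by assignment on EMA-completed days. Interpret only the framing main effect from it: the planning prompt precedes that EMA, so planning terms would be conditioned on a later event.

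**Cost.** A few sentences and a slightly less favourable stated effect. If delivery is gated, the assigned-days estimate is somewhat diluted and one supporting analysis is added. N, schedules and data collection do not change.

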3.0 STUDY DESIGN

3.1 Overview of Study Design

For this project, we will enroll 50 participants diagnosed with renal cell carcinoma or gastrointestinal cancer in an eight-week study. Using a micro-randomized design, participants will receive affective framing messages and intention planning prompts on a randomized schedule, such that participants will receive each message type on 50% of days.

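### The Hypothesis 2a/2b model fixes the message effects and states no robust variance, so the standard error of the average effect is too small if response varies between participants

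*Combined protocol and SAP*

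**What the plan says.** Section 7.0, Hypothesis 2a, sets up a mixed model for daily steps "with participant and time as random effects and other effects as fixed". The message indicator is placed among the fixed terms: "main effects of affective framing intervention (message/no message) and linear time effects will be within-subjects factors". The model also has message-by-time and framing-by-planning interactions. For 2b: "The same repeated-measures mixed effects model described for Hypothesis 2a will be used for this hypothesis", so the planning effect is fixed as well.

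No section mentions a random message slope, a robust or clustered variance, or a sensitivity analysis for response that differs between participants. The coding of time and of the indicators is not stated. Under Power calculations, the 2a/2b sample sizes are those "which assume 80% power with an alpha=0.05". The effect is assumed constant over the 56 days, and nothing is said about constancy across participants.

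**The concern.** A fixed message effect is one common value for all participants. If the true effects differ, the estimated average carries an extra variance component from having sampled only 50 people. A model without a random message slope leaves nearly all of that component out of its standard error. The random time effect does not pick it up, because messages are randomised day by day within each participant.

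At stake are the interval and test for the average framing and planning effects. Section 1.0 makes efficacy, together with acceptability, the basis for deciding which strategies enter the adaptive intervention.

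**Working it through.** **Inputs.** N = 50 (section 3.1), T = 56 days, message probability 0.5, alpha 0.05, power 80% and target effect d = 0.109 (section 7.0, Power calculations). Effects are in units of the within-person residual SD, set to 1. The between-participant SD of the effect, τ, is not in the documents and is varied as an assumption.

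**Step 1: the plan's own table.** Use an F test with 1 and N − 2 degrees of freedom and noncentrality N × T × 0.5 × 0.5 × d². At N = 50 and d = 0.109 the noncentrality is 50 × 56 × 0.25 × 0.011881 = 8.317 and power is 0.81. For effect sizes 0.200, 0.109, 0.099, 0.091 and 0.076 the smallest N with 80% power is 17, 50, 60, 70 and 100, an exact match to all five rows. Person-day degrees of freedom would give 15, 48, 58, 68 and 98. The planning therefore used participant-level degrees of freedom, but no between-participant variance in the effect.

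**Step 2: the standard error when τ > 0.** With centred coding, one participant's message contrast has sampling variance 4/56 = 0.0714.

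- Variance reported by the fixed-effect model: about (4/56)/50.
- True variance of the average effect: (4/56 + τ²)/50.
- Ratio of true to model SE: R = √(1 + 14τ²).
- Understatement of the SE: 1 − 1/R.
- Type I error for a zero average effect: 2[1 − Φ(1.96/R)].

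| τ (assumed) | 1 + 14τ² | R | SE understated by | Type I error |
|---|---|---|---|---|
| 0 | 1.000 | 1.000 | 0% | 5.0% |
| 0.05 | 1.035 | 1.017 | 2% | 5.4% |
| 0.10 | 1.140 | 1.068 | 6% | 6.6% |
| 0.15 | 1.315 | 1.147 | 13% | 8.7% |
| 0.20 | 1.560 | 1.249 | 20% | 11.7% |

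The fitted residual absorbs a little of the variation (a factor 1 + τ²/4). Allowing for it changes the last row only from 11.7% to 11.5%.

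**Step 3: simulation.** A REML fit had a random intercept, a random time slope, and fixed message, time, planning and both interaction terms, all centred, with 400 to 600 trials per setting (Monte Carlo error about 1 percentage point). It rejected a zero average effect in 3% to 6% of trials at τ = 0, 6.0% to 6.5% at 0.10 and 10.8% at 0.20. A second simulation gave 6.3% and 12.7% at 0.10 and 0.20, while a participant-clustered standard error stayed near 5%. Adding a random message slope gave 2.8% to 4.2% at τ = 0 and 4.5% to 4.8% at 0.10 to 0.20.

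**Step 4: dependence on coding.** With uncentred time and the message-by-time term in the model, the message main effect is the day-0 effect. Its sampling variance is about four times larger, so R = √(1 + 3.5τ²) and type I error is about 5.4% at τ = 0.10 and 6.6% at 0.20. If only the planning indicator is uncentred (0/1), the variance doubles, R = √(1 + 7τ²), and the figures are 5.8% and 8.3%.

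**Step 5: power with a valid standard error.** The noncentrality becomes N × d²/(4/56 + τ²). At N = 50 and d = 0.109 it is 8.317, 7.295 and 5.331 for τ = 0, 0.10 and 0.20. Power is 0.81, 0.75 and 0.62, and the N for 80% power is 50, 56 and 76.

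**The case against.** The size rests on an SD that the documents do not supply. At τ = 0.10, close to the whole target effect of 0.109, the error rate is under 7%. At τ = 0.20 the SD is nearly twice that effect (0.20/0.109 = 1.8), and a zero average then needs real gains in some participants offset by real losses in others. This is also a pilot whose first aim is feasibility. These points stand, and they limit the size of the problem.

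Four stronger readings are tempting, and the documents do not support them.

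- **That the plan itself expects people to respond differently.** The exploratory section says "Our ultimate goal is to be able to evaluate these factors to inform decision rules in the ultimate adaptable intervention", but those factors are daily assessments that vary over time, and section 1.0 describes adaptation by when support is given. Stable differences between people are plausible but not asserted.
- **That the inflation reaches 18% at τ = 0.20.** That needs a residual variance of 0.5, from the correlation of 0.5 that the plan states only for Hypothesis 2c. The 2a/2b table is reproduced with residual variance 1.
- **That messages with no effect on anyone would pass too often.** If nobody responds, τ = 0 and the error rate stays at 5%.
- **That the plan overlooks having only 50 people.** The sample-size table uses participant-level degrees of freedom.

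Section 7.0 also cites a methods paper for the model. Whether that paper supplies a robust variance cannot be checked from the documents. If one is intended, a sentence in the SAP would settle the matter, because the present wording does not say so.

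**Conclusion.** The point holds as a conditional one. Followed as written, the 2a/2b analysis understates the standard error of the average message effect whenever response varies between participants. With centred coding the inflation is small for a between-participant SD up to about 0.10 (type I error at most about 6.6%) and material by 0.20 (about 11.7%, SE understated by about 20%). With uncentred time it is about 5% to 7% over SDs of 0.10 to 0.20. These figures assume a zero average effect with varying individual effects, residual variance 1 and complete 56-day records. The direction is certain for any SD above zero, but the size is not known. The change is worth making because it is cheap and brings the analysis into line with the participant-level degrees of freedom behind the plan's own table.

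**What to change.** - For 2a and 2b, prespecify participant-clustered robust standard errors with a small-sample correction and a t reference on participant-level degrees of freedom. Alternatively, add participant-level random slopes for the framing and planning indicators, with the clustered standard error as the fallback if they do not converge.
- Centre time and both indicators, and state the coding, so that each main effect is the average effect the hypothesis refers to.
- Show 2a/2b power over a range of between-participant SDs: at d = 0.109 and N = 50, about 0.81 at SD 0, 0.75 at 0.10 and 0.62 at 0.20.

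The cost is SAP wording and a model option, with no new data. The downsides are wider intervals and lower stated power when response varies, possible convergence problems with random slopes, and a slightly conservative random-slope test if there is no variation (simulated 2.8% to 4.2%).

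### Hypotheses 2a and 2b are read from main effects in a model with interactions, but time origin, message coding and the tested contrast are not stated; counting time from day 0 or 1 would cut 2a power from about 81% to between 24% and 30%

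*Combined protocol and SAP*

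**What the plan says.** Section 7.0 words Hypotheses 2a and 2b as a comparison of daily steps on days with and without the message. Neither is limited to a particular study day or to days without the other prompt.

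The model for 2a contains the framing main effect and linear time, and "an intervention by time interaction term will be included". It also contains the planning prompt as a time-varying covariate, and "an affective framing by planning message interaction will be included to assess synergistic effects of the two messages". The same model serves 2b: "Only the interpretation of the results will be different as the presence/absence of the implementation message will be the main effect".

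The power section rests on values "which assume 80% power with an alpha=0.05" and on the assumption that the "effect size (standardized difference between treatment groups, similar to Cohen's d) is constant during the 56-day study period". Its table gives a detectable effect of 0.109 at 50 participants, which is the number in section 3.1: "we will enroll 50 participants diagnosed with renal cell carcinoma or gastrointestinal cancer in an eight-week study".

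The plan gives no numeric coding for either message and no origin for time. It does not say which coefficient or contrast decides 2a or 2b.

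**The concern.** Once a variable enters an interaction, its own coefficient is the effect where the interacting variables equal zero. With days numbered from 0 or 1, the framing coefficient is the effect at the very start of the study, extrapolated to day 0 if numbering starts at 1. With 0/1 messages it is also restricted to days without a planning prompt. The 2b planning coefficient, with 0/1 messages, is the effect on days without a framing message.

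These coefficients are much less precise than the study-average contrast that the sample size was chosen for. Section 1.0 says that acceptability and efficacy will decide which components enter the adaptive intervention. A component with the planned effect could therefore look ineffective because of a coding choice that nobody wrote down. Leaving the contrast open also allows the deciding test to be chosen after the data are seen.

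**Working it through.** **Inputs.** From the power section: effect d = 0.109 in SD units, constant over time; 56 days; daily message probability 0.5; alpha 0.05; 80% power. From section 3.1: N = 50. Sidedness is not stated; a two-sided test reproduces the table. Assumptions added here: all 56 days usable, independent schedules for the two messages, independent residuals after the participant effect, and zero true interactions.

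**Step 1: reproduce the plan's figure.** For a single message contrast with no interactions, the variance of the estimate is 4/(N × 56) in SD² units. The noncentrality is

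λ = N × 56 × 0.25 × d² = 50 × 56 × 0.25 × 0.109² = 700 × 0.011881 = 8.32.

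A noncentral F with 1 and N − 2 = 48 df gives 80.7% power. The same formula returns exactly the tabulated 17, 50, 60, 70 and 100 participants for effects 0.200, 0.109, 0.099, 0.091 and 0.076. The table is thus matched by a one-parameter, study-average test without interaction terms.

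**Step 2: variance inflation of the tested coefficient.** For 56 consecutive days the variance of time is (56² − 1)/12 = 261.25. Its mean is 27.5 when counted 0-55 and 28.5 when counted 1-56. With independent 1:1 schedules, the variance of a message coefficient relative to 4/(N × 56) is

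1 + (mean of time)²/261.25 [if that message has a time interaction] + 1 [if the other message is coded 0/1 and the product term is present].

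- Time interaction, day 0: 1 + 756.25/261.25 = 3.89
- Time interaction, day 1: 1 + 812.25/261.25 = 4.11
- Both terms, 0/1 messages: 4.89 (day 0) and 5.11 (day 1)
- Product term only, 0/1 messages: 2.00
- Time centred and messages −0.5/+0.5: 1.00

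Simulated blocked schedules for 50 participants, with participant means removed, give almost the same values: 3.90, 4.11, 4.92, 5.14, 2.02 and 1.00.

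**Step 3: power at d = 0.109.** Divide λ by the simulated inflation and use the same F test. For example, 8.32/4.92 = 1.69, which gives 24.7%.

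| Coefficient tested | Inflation | Power |
|---|---|---|
| 2a, 0/1 messages, time from day 0 | 4.92 | 24.7% |
| 2a, 0/1 messages, time from day 1 | 5.14 | 23.9% |
| 2a, −0.5/+0.5 messages, time from day 0 | 3.90 | 29.9% |
| 2a, −0.5/+0.5 messages, time from day 1 | 4.11 | 28.6% |
| 2a, 0/1 messages, time centred | 2.02 | 51.1% |
| 2b, 0/1 messages, time interaction for framing only | 2.02 | 51.1% |
| 2b, −0.5/+0.5 messages, time interaction for framing only | 1.00 | 80.6% |
| 2a or 2b, −0.5/+0.5 messages, time centred, all interactions kept | 1.00 | 80.6% |

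A normal approximation moves these by at most about two points (82.2% in place of 80.7%, 25.5% in place of 24.7%).

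**The case against.** The strongest reply is that the plan specifies neither 0/1 coding nor a day-0 origin. Its wording for the messages names the levels of a factor, and in factorial usage a main effect is averaged over the other factor. The hypotheses themselves describe the averaged contrast. The model is also referred to a 2015 publication that is not available here and may settle the coding.

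Much of this stands. It would be wrong to conclude that the plan as described has 24% power, or that including the interactions costs power: with centred terms they cost none. Nor does the low figure carry over to both hypotheses. The time interaction is written for framing, so the 2b coefficient is not a start-of-study effect; it would drop to about 25% only if an uncentred planning-by-time term were added, which the plan does not list. The 24% and 51% figures belong to different contrasts and do not form a range for one quantity. Under the plan's assumption of a constant effect, and with no framing-by-planning interaction, the conditional and averaged effects have the same value; only the precision differs.

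What the reply does not remove is the time problem for 2a. Factorial coding of the messages does not help there, because time enters as a linear term: the framing coefficient is still evaluated at time zero, and power is 29-30% unless time is centred or the effect is averaged over days. The plan's text states neither step.

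**Conclusion.** The concern holds as a conditional one. Section 7.0 leaves the deciding contrast for 2a and 2b undefined, and ordinary day numbering would lead to a far weaker test of 2a than the power section claims: about 24-25% with 0/1 messages, or 29-30% with −0.5/+0.5 messages, against 80%. For 2b the exposure is about 51% with 0/1 messages and none with −0.5/+0.5.

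The size rests on the assumptions listed with the inputs. The statement that "the proposed sample size of 50 will be able to detect effect sizes" of about half a small effect is correct for the study-average contrast, so the sample size does not need to change. A reader might infer that the trial is underpowered or that the interactions should be dropped. The documents support neither inference.

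**What to change.** In section 7.0, state that time is centred at mid-study and that both messages are coded −0.5/+0.5. Equivalently, define the 2a and 2b tests as the message-versus-no-message contrast averaged over the 56 days and over the other message. Keep framing-by-time and framing-by-planning as secondary terms. If a quadratic message-by-time term is added, which the plan's allowance for more complex time effects leaves open, use the averaged-contrast wording, since the coefficient at mid-study is then no longer the 56-day average.

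The cost is a sentence or two of analysis-plan wording. Data, model, number of parameters and sample size stay the same, and power for both hypotheses is about 81% at d = 0.109.
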